Sample size was calculated using data from previous studies that examined changes in FEV₁ in people with EIB. Two studies by Anderson et al., in 2001 used a similar crossover design and found a detectable difference of 12% reduction in FEV₁ with a standard deviation of 14%. Calculation for a crossover design based on analysis of variance F-tests using these values with a power of 0.8 and an alpha level of 0.05 led to a sample size of 24 subjects. Previous data from FeNO in an asthmatic population were considered to make sure this sample size would be appropriate for FeNO measurement. Changes in FeNO measurements biased on a study by Niu et al., in 2018 showed a larger effect size than FEV₁ so the sample size based on FEV₁ measurement is more conservative.

Measures/Instruments

The two independent variables in this study are ozone pollution status and medication (salbutamol) status. Both independent variables will have a nominal level of measurement with two levels. The two levels of ozone air pollution are: 170 ppb ozone and room air. Room air in the lab where data collection will be done has low levels of ozone (typically less than 10 ppb) and other pollutants. While wearing nose clips, participants will be exercising on a stationary bike breathing in air from a mouthpiece that is connected to a sealed chamber. The sealed chamber will contain an ACT-5000 ozone generator (ACT-series, 2021). The ozone generator will either be turned on or off depending on the allocated treatment. The concentration of ozone will be

confirmed using an electrochemical ozone sensor that will be set up in the chamber. Electrochemical ozone sensors have been validated using linear association models that have reported R^2 values of 0.98 (Afshar-Mohajer et al., 2018). For the salbutamol condition, participants will take two puffs from a meter dose inhalers (MDI) designed to deliver 100 μg of salbutamol per puff or a trainer MDI for the placebo condition. To ensure reliability of the dose delivered participants will be told standardized instruction for using an MDI. Adhering to these instructions increases the consistency of the dose delivered (Sanchis et al., 2013). In addition, an aerochamber will be attached to the MDI which further increases dose consistency (Newman, 2004). Medication status will have two levels: 200 μg of salbutamol and placebo salbutamol.

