Rating of symptoms (dyspnea, cough, sore throat, headache, chest pain, and chest tightness) and blood pressure will also be measured. The selected symptoms were chosen because they have been recognized or are related to symptoms of ozone exposure (Lippmann, 1989). Dyspnea will be measured subjectively using a modified Borg scale that has previously been used to measure dyspnea and validated against other dyspnea measures (Gaber et al., 2019). The other symptoms will be subjective rated on a scale from 0-5. Blood pressure will be measured using an automated sphygmomanometer. In accordance with Hypertension Canada's guidelines on blood pressure measurement, blood pressure will be measured three times and the first measure will be thrown away while the latter two are averaged (Nerenberg et al., 2018).

Study Design

This research design can be characterized as a placebo-controlled crossover design with pre-post measures. There are two independent variables: ozone pollution status and medication status. The two levels of ozone pollution status are 170 ppb ozone and room air. The two levels of medication status are 200 µg of salbutamol and placebo medication. Participants will perform 30 minutes of submaximal exercise at 60% of their $VO_{2\max}$ in all four conditions. These conditions are salbutamol + ozone, placebo + ozone, salbutamol + room air, and placebo + room air. The order of the conditions on the experimental days will be randomized to one of four sequences. The four conditions will be labelled A (ozone + inhaler A), B (ozone + inhaler B), C (room air + inhaler A), and D (room air + inhaler B). The researchers will not know which inhaler (A or B) is placebo

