and which is salbutamol to facilitate blinding. The four condition sequences will be ABCD, BDAC, CABD, DCBA. These sequences represent a Latin Square crossover design, which is uniform both within periods and within sequences. In other words, each condition appears only once in each sequence and only once at a particular spot within the four sequences. This means that the sequences are balanced with respect to first order carry over effects because each condition precedes every other condition only once. For example, condition D is first only once and is preceded by condition A, B, and C only once. FeNO, spirometry, blood pressure, and symptom measures will be obtained before and immediately after, 30 minutes after, and 1 hour after exercise in each condition. Pre and post measures will be compared from the four conditions to examine how exercising in different combinations of ozone pollution and medication influence pulmonary function (spirometry) and inflammation (FeNO). The medication condition will be double blinded to control for the placebo effect and expectancy bias of the research. This will be done by having a placebo inhaler and a salbutamol inhaler labeled A and B by someone who is not collecting data. That way neither the participant nor the researcher collecting data will know whether placebo or real salbutamol is being used in a particular condition. The ozone condition will also be double blinded. This will be done by having the participant breathe air from a tube connected to a sealed chamber, which they will not be able to see inside, that has an ozone generator that is controlled on the opposite side of the chamber. A separate researcher will be controlling the ozone chamber and on room air will pretend to operate the generator for the room air conditions and actually operate the generator for the ozone conditions. Ozone levels will be recorded for all conditions and revealed to the main researcher after data collection is completed.

Procedures

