in subsequent trials at 60% of $VO_{2\max}$. A graded exercise test with a ramp protocol will be performed while expired gas is analyzed using a metabolic cart to measure $VO_{2\max}$ (Beltz et al., 2016). Participants will conduct a self-selected warm-up. Following the warm up, participants will start the exercise test at 75 or 100 Watts, with the workload increasing in a step-wise fashion by 10 or 20 Watts every two minutes until they feel that they can no longer continue or until they can no longer maintain a cadence of 60 rotations per minute (rpm). $VO_{2\max}$ will be considered achieved if three of the following four criteria are met: heart rate (HR) $>90\%$ of age-predicted maximum, respiratory exchange ratio >1.15 , plateau of oxygen consumption per minute (VO_2) with increasing work load, and volitional exhaustion (Beltz et al., 2016). Age-predicted maximum heart rate will be calculated as $220 - \text{age (years)}$.

Participants will return to the lab on four separate occasions to complete the four exercise trials in a random order. During each visit, participants will take two puffs from an MDI, wait 15 minutes, and then pre-exercise measures will be taken. Pre-exercise FeNO, blood pressure, and symptoms will be measured and then participants will put on a headset that includes a mouth piece that will be used for spirometry and will control inspired air during exercise. Pre-exercise spirometry will be measured and then participants will perform a self-selected warm-up. Once they are ready, participants will exercise at a resistance that will elicit 60% of their $VO_{2\max}$ for 30 minutes while breathing through a one-way valve connected to a sealed chamber. The chamber will either contain room air or 170 ppb ozone being generated by an ozone generator. After 5 minutes and 25 minutes of exercise participants will do an IC. After 30 minutes are complete, post-exercise blood pressure, symptoms, spirometry and FeNO will be measured. All visits will be separated by 48 hours to prevent carryover effects from previous exposure to ozone or salbutamol.

This 48-hour duration was chosen because it is longer than five half-lives of salbutamol medication.

Ethical Considerations

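### No covariate adjustment is specified for the pre-exercise reading taken before ozone at every visit; it could sharpen the ozone and ozone-by-salbutamol contrasts, by an amount the documents do not fix

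*Combined protocol and SAP*

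**What the plan says.** The Study Design section describes a "placebo-controlled crossover design with pre-post measures" with four conditions: ozone or room air, crossed with salbutamol or placebo. FeNO, spirometry, blood pressure and symptoms are "obtained before and immediately after, 30 minutes after, and 1 hour after exercise in each condition". On how these are to be analysed, it says that "Pre and post measures will be compared from the four conditions". It gives no model, covariate, definition of change or primary contrast.

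The only statistical method named is in the sample-size paragraph under Sample and Recruitment: "Calculation for a crossover design based on analysis of variance F-tests using these values". The values are that earlier studies "found a detectable difference of 12% reduction in FEV₁", "with a standard deviation of 14" per cent, and the calculation "with a power of 0.8 and an alpha level of 0.05 led to a sample size of 24 subjects".

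The Procedures section fixes the order at each exposure visit. The inhaler is taken and 15 minutes pass. Then "Pre-exercise FeNO, blood pressure, and symptoms will be measured", followed by pre-exercise spirometry, and only then does the participant exercise on ozone or room air.

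**The concern.** Each visit supplies a reading of both main outcomes that the visit's ozone cannot have affected. FeNO and FEV₁ vary from day to day within a person, and the crossover removes only the stable differences between people. The remaining visit-to-visit variation stays in the error term unless the analysis uses the pre-exercise value efficiently. Subtracting it (a change score) adds noise when the correlation is low. Ignoring it (post-exercise values only) wastes information when the correlation is high. Covariate adjustment does at least about as well as either.

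The interaction is where this matters most. It separates what salbutamol does in ozone from what it does in room air, and it has the least power of the contrasts considered here.

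**Working it through.** **Inputs.** From the sample-size paragraph: difference 12, SD 14, N = 24, alpha 0.05, power 0.80. Assumed, because the documents do not give them: the within-person correlation rho between pre- and post-exercise values across visits; equal within-person variance before and after exercise; 14% as the per-visit SD of change; and 12 points as the size of each contrast, including the interaction.

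**The plan's own figure.** Take SD 14 per visit with no correlation between visits. The SD of a two-condition difference is 14 × √2 = 19.8. A paired t-test (two-sided 0.05, noncentral t) then needs n = 24, with power 0.811, so the plan's number reproduces. If 14 were the SD of the paired difference, n would be 13, which does not match.

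**Variance formulas.** With unit within-person variance before and after exercise:
- post-exercise value only: 1
- change score: 2(1 − rho)
- adjusted: 1 − rho²

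Adjusted relative to change: (1 − rho²) / [2(1 − rho)] = (1 + rho)/2, which is 0.75 at rho = 0.5.

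**Unadjusted standard errors (N = 24).**
- Ozone versus room air within one medication: 14 × √2 / √24 = 4.04
- Ozone-by-salbutamol: 14 × √4 / √24 = 5.72
- Ozone averaged over inhalers: 14 / √24 = 2.86

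The adjusted standard error is multiplied by √((1 + rho)/2), with 22 degrees of freedom instead of 23.

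| Contrast | Change score | rho 0.3 | rho 0.5 | rho 0.7 | rho 0.9 |
|---|---|---|---|---|---|
| Ozone vs room air, one medication | 0.81 | 0.94 | 0.91 | 0.87 | 0.83 |
| Ozone-by-salbutamol | 0.52 | 0.70 | 0.64 | 0.59 | 0.54 |

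For ozone averaged over inhalers, power is already 0.980 and becomes 0.996 at rho 0.5, a gain of 1.6 points.

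**Unequal variances.** Let k be the ratio of pre-exercise to post-exercise within-person SD. Adjusted relative to change is (1 − rho²) / (1 + k² − 2·rho·k), which equals 1 when k = rho. At rho 0.5, starting from interaction power 0.52 and pairwise power 0.81:
- k = 1.0: 0.64 and 0.91
- k = 0.8: 0.57 and 0.85
- k = 0.7: 0.54 and 0.83
- k = 0.5: 0.52 and 0.81, no gain

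**Against either unadjusted analysis.** The full crossover was simulated with participant and period effects and the sequences as printed (4,000 runs). Interaction power for change score, post-only and adjusted was:
- rho 0: 0.49, 0.78, 0.77
- rho 0.5: 0.50, 0.48, 0.59
- rho 0.8: 0.49, 0.23, 0.52

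These fall slightly below the closed-form values because the printed sequences place B twice in the third period and D twice in the fourth, so removing period effects costs some information.

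**Validity.** The two visits in an ozone versus room-air comparison within one medication share the same inhaler. In the interaction, a salbutamol shift in the pre-exercise value that is the same on ozone and room-air visits cancels. In a separate simulation with a shift of 6 in both pre and post values and a true interaction of 12, the mean adjusted estimate was 12.0 to 12.1. With no interaction, the rejection rate at rho 0.5 was 0.06 adjusted and 0.054 for change scores.

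**The case against.** The strongest objection is that the plan has not made the choice being criticised. A reader might infer that it commits to change scores, since it speaks of pre and post and sizes the trial on a percent reduction. The documents do not support that: the ANOVA F-tests belong to the sample-size calculation, and the sentence on comparing measures is compatible with covariate adjustment. This stands. The point is that adjustment is unspecified, within the wider gap that no analysis model is stated.

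Second, the plan's hypothesis compares salbutamol with placebo in ozone, and the adjustment cannot be used there. This also stands. The benefit falls on the ozone and interaction contrasts only, and the plan names neither as primary.

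Third, the size of the gain rests on borrowed inputs. The 12 and 14 come from FEV₁ studies in EIB. No ozone or interaction effect size is given, nor any FeNO SD or pre-post correlation. Percent reductions are already scaled to a baseline, so the absolute-change formulas are approximate. Post-exercise readings in people screened for a fall in FEV₁ may well vary more than pre-exercise ones, which can erase the gain over change scores. All of this limits the size claimed; it does not make the adjustment invalid or materially worse than either alternative.

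Fourth, a reader might infer that salbutamol versus placebo should therefore use post-exercise values alone. That does not follow and could be costly. On the same inputs the post-exercise SD is 14/√(2(1 − rho)), and power for a 12-point difference falls from 0.81 with change scores to 0.60 at rho 0.7 and 0.25 at rho 0.9.

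**Conclusion.** The plan omits a valid, nearly free gain in precision for the ozone versus room-air contrasts and the ozone-by-salbutamol interaction. Its size is not known from the documents. Under the stated assumptions the gain over change scores is about 13 down to 2 points for ozone versus room air within one medication, and about 18 down to 2 points for the interaction, as the within-person correlation goes from 0.3 to 0.9. It can be near zero if the pre-exercise reading varies less than the post-exercise one. It is under 2 points at rho 0.5 for ozone averaged over inhalers, and there is none for salbutamol versus placebo.

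A reader might take the 10 to 12 points at a correlation of 0.5 as the loss built into this plan. The documents do not support that: the correlation, the equal variances and the 12-point effect are all assumed. The correlation must also be the within-person one across visits; an ordinary between-person correlation of 0.5 would not give this gain. The case for the change rests on its validity and low cost, not on one power figure.

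**What to change.** State the FeNO and spirometry analysis before unblinding. For ozone versus room air and for ozone-by-salbutamol, model each post-exercise value with participant, period and condition, plus that visit's pre-exercise value as a covariate. Make the slope within-person, either by fitting participants as fixed effects or by adding the participant's mean pre-exercise value.

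State that salbutamol versus placebo contrasts are not adjusted for this reading, because it follows the inhaler and adjustment could remove part of the drug effect. Whether those contrasts use change or post-exercise values is a separate decision that this fix leaves open, but the plan should record it.

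The cost is wording and one degree of freedom; no new data are needed. There will be separate model statements for the ozone and interaction contrasts and for the salbutamol contrasts. The reported interaction therefore need not equal the difference between the reported salbutamol effects, and the plan should say so in advance.
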